### **2.8.1.2 Deaths**

Adverse events leading to death will be summarized with number and percentage by treatment and primary AE (SOC and PT). Similar summary on adverse events leading to death that is suspected to be related to study treatment will also be provided. Listing of death will also be provided.

### **2.8.1.3 Adverse events reporting for CT.gov and EudraCT**

For the legal requirements of clinicaltrials.gov and EudraCT, two required tables on treatment emergent adverse events which are not serious adverse events with an incidence greater than 2% and on treatment emergent serious adverse events and SAE suspected to be related to study treatment will be provided by system organ class and preferred term on the safety set including all data up to EoS based on the final DBL.

If for a same patient, several consecutive AEs (irrespective of study treatment causality, seriousness and severity) occurred with the same SOC and PT:

- a single occurrence will be counted if there is  $\leq 1$  day gap between the end date of the preceding AE and the start date of the consecutive AE
- more than one occurrence will be counted if there is  $> 1$  day gap between the end date of the preceding AE and the start date of the consecutive AE

For occurrence, the presence of at least one SAE / SAE suspected to be related to study treatment / non SAE has to be checked in a block e.g., among AE's in a  $\leq 1$  day gap block, if at least one SAE is occurring, then one occurrence is calculated for that SAE.

The number of deaths resulting from SAEs suspected to be related to study treatment and SAEs irrespective of study treatment relationship will be provided by SOC and PT.

## 2.8.2    **Laboratory data**

Laboratory tests will be conducted by local lab. Clinically significant abnormal results will be reported as adverse events and included in the AE summaries; however the following liver enzyme testing results will be entered into the clinical database:

- Alanine aminotransferase (ALT)
- Aspartate aminotransferase (AST)
- Total bilirubin (TBIL) / Direct bilirubin
- Alkaline phosphatase (ALP)

Number (%) of newly occurring liver enzyme abnormalities, as listed below, at any time during post-treatment will be provided. A newly occurring event is when a patient not meeting a given criterion at baseline but meeting the corresponding criterion during post-baseline.

- ALT or AST  $> 3.0x, 5.0x, 10.0x, 20.0x$  ULN
- ALP  $> 1.5x$  ULN
- TBIL  $> 1.5x, 2.0x$  ULN
- ALT or AST  $> 3.0x$  ULN & TBIL  $> 1.5x$  ULN
- ALT or AST  $> 3.0x$  ULN & TBIL  $> 2.0x$  ULN

The last two criteria on the list are based on the maximum post-baseline ALT, AST, and TBIL.

An eDISH plot on the maximum post-baseline ALT value relative to the ULN and TBIL value relative to the ULN will also be provided at log-log scale.

### Hematology parameters

The hematology parameters include absolute neutrophil count, monocytes, lymphocytes measured from local lab. The post baseline value and the percent change from baseline at post baseline are summarized by mean, SD, median, Q1, and Q3. The summary is based on the observed data.

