### **Potential risks due to study medication**

The risk to patients in this trial will be minimized by adherence to the eligibility criteria and close clinical monitoring, including by an internal DMC. Over 2,600 patients including approximately 480 children (aged 2 to 17 years) have been treated with canakinumab in interventional studies in Periodic fever syndromes, Still's disease, gouty arthritis, or other IL-1 beta mediated diseases, and healthy volunteers. The most frequently reported adverse drug reactions were infections, predominantly of the upper respiratory tract. The majority of the events were mild to moderate although serious infections were observed. No impact on the type

or frequency of adverse drug reactions was seen with longer-term treatment. Hypersensitivity reactions and opportunistic infections have been reported in patients treated with canakinumab. Neutropenia and leukopenia has also been observed with IL-1 inhibitors including canakinumab, with transient decreases to  $<1 \times 10^9$  /L observed during clinical trials with canakinumab.

In addition to experience in approved indications, over 10,000 patients were enrolled in the CANTOS study evaluating canakinumab for the prevention of recurrent cardiovascular events among stable post-myocardial infarction patients with elevated CRP, with a cumulative exposure of 32662.6 patient-years (21745.1 patient-years for total canakinumab and 10917.5 patient-years total for placebo).

No clinically meaningful differences between canakinumab and placebo were observed for most safety topics of interest, apart from an increase in serious infections and of fatal infections/sepsis; however, the overall incidence was low. The pattern of infections was stable over time, with very few confirmed opportunistic infections distributed evenly across the treatment groups. There was no evidence of tuberculosis reactivation in canakinumab-treated patients.

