The overall incidences of investigator-reported infection AEs and discontinuations due to infection AEs were comparable across the treatment groups. For investigator-reported infection SAEs, there were numerical differences of 1-2% in the overall incidence for the canakinumab 300 mg and 150 mg groups compared with placebo. Similarly, a slightly higher percentage of patients discontinued due to an infection SAE in the canakinumab 300 mg and 150 mg groups than in the placebo group. The majority of infection AEs consisted of non-serious upper respiratory tract infections which showed no clinically meaningful differences across the treatment groups. Increases in the order of 1% with canakinumab relative to placebo in the overall population were seen for certain infection events, i.e., sepsis, cellulitis, infectious pneumonias. The increase in cellulitis was seen predominately in patients with type-2 diabetes mellitus, and that of infectious pneumonias in patients with a history of asthma/chronic obstructive pulmonary disease. There was no meaningful difference between canakinumab 150 mg and 300 mg in the risk of cellulitis or infectious pneumonias; however, a higher risk of sepsis AEs with canakinumab 300 mg was observed.

Laboratory data showed an increase with canakinumab 300 mg only in mild neutrophil and platelet count abnormalities (Grade 1), with no imbalances in larger declines (Grades 2-4) in neutrophil and platelet counts, or in triglyceride levels, between 300 mg and 150 mg.

All-cause mortality was numerically lower across the three canakinumab treatment groups compared to placebo, with both fewer cardiovascular deaths and non-cardiovascular deaths. There was an increased incidence of deaths due to infection/sepsis for canakinumab 150 mg vs. placebo, although the numbers of related deaths were low overall.

The main adverse drug reaction was infection, of which the most common included viral upper respiratory tract infection, influenza, and pneumonia.

Overall, the safety and tolerability profile of canakinumab in post myocardial infarction patients was consistent with the known safety profile in the approved indications.

Known risks of canakinumab pertinent to short term use include the risks of infection (including opportunistic infection), interaction with live vaccines and the use in combination with other

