### 5.2 Exclusion criteria

Participants meeting any of the following criteria are **not** eligible for inclusion in this study.

1. History of hypersensitivity to canakinumab or to biologic drugs.
2. Intubated and on mechanical ventilation (invasive) at time of randomization
3. Treatment with immunomodulators or immunosuppressant drugs, including but not limited to tocilizumab, TNF inhibitors and anti-IL-17 agents within 5 half-lives or 30 days (whichever is longer) prior to randomization with the exception of anakinra which is excluded within 5 half-lives only. *Note: Immunomodulators (topical or inhaled) for asthma and atopic dermatitis and corticosteroids (any route of administration) are permitted*
4. Suspected or known untreated active bacterial, fungal, viral, or parasitic infection with the exception of COVID-19
5. Neutropenia with ANC  $< 1000/mm^3$
6. Any serious medical condition or abnormality of clinical laboratory tests that, in the investigator's judgment, precludes the patient's safe participation in and completion of the study
7. In the opinion of the investigator, progression to death is imminent and highly likely within the next 24 hours, irrespective of the provision of treatments
8. Current participation in any other investigational trials

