#### **Hematology**

Hemoglobin, hematocrit, red blood cell count, white blood cell count with differential, and platelet count will be measured according to the assessment schedule in [Table 8-1](#).

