### **Clinical laboratory evaluations**

Laboratory data will be summarized by treatment and visit.

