**Table 1-1 Objectives and related endpoints**

Objective(s)	Endpoint(s)
Primary Objective  To demonstrate the benefit of canakinumab + standard of care (SOC) in increasing chance of survival without ever requiring invasive mechanical ventilation among patients with COVID-19-induced pneumonia and CRS	Endpoint for primary objective:  Clinical response, defined as survival without ever requiring invasive mechanical ventilation from Day 3 (inclusive) up to Day 29 (inclusive).
Secondary Objective(s)  To demonstrate the benefit of canakinumab in reducing 4-week case fatality rate (CFR) among patients with COVID-19-induced pneumonia and CRS regardless of other subsequent clinical interventions	Endpoint(s) for secondary objective(s):  COVID-19-related death during the 4-week period after study treatment
To evaluate change in clinical serologic measurements related to CRS in COVID-19 patients with pneumonia	Adjusted geometric mean ratio to baseline overtime up to Day 29 in the following clinical chemistry measurements: 

○ C Reactive Protein (CRP)

○ Serum ferritin

○ D-dimer

To evaluate safety of canakinumab in patients with COVID-19-induced pneumonia and CRS	Number of participants with Adverse Event (AE), serious adverse events (SAE), clinically significant changes in laboratory measures, and vital signs

Objective(s)	Endpoint(s)

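### SAP 2.8.2 gives neutrophils no minimum and no threshold count, so patients with low counts are counted only if an investigator reports an adverse event

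*SAP*

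**What the plan says.** The safety endpoint in SAP Table 1-1, repeated from Protocol Table 2-1, is "Number of participants with Adverse Event (AE), serious adverse events (SAE), clinically significant changes in laboratory measures, and vital signs".

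On risk, Protocol 4.5 states: "Neutropenia and leukopenia has also been observed with IL-1 inhibitors including canakinumab". It adds that transient falls below 1 x 10^9/L were seen in trials. For the large cardiovascular study it reports: "Laboratory data showed an increase with canakinumab 300 mg only in mild neutrophil and platelet count abnormalities (Grade 1"), with no imbalance in Grades 2 to 4 between 300 mg and 150 mg. Exclusion criterion 5 begins "Neutropenia with ANC" and sets the limit at 1000/mm3.

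On collection, Protocol 8.4.1.2 covers haemoglobin, haematocrit and red cells, plus "white blood cell count with differential, and platelet count will be measured according to the assessment schedule". Table 8-1 marks hematology as recorded in the clinical database, every other day while the patient is in hospital.

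On analysis, Protocol 12.5.3 says: "Laboratory data will be summarized by treatment and visit", without restricting it to certain tests. SAP 2.8.2 is narrower: "The hematology parameters include absolute neutrophil count, monocytes, lymphocytes measured from local lab". It then lists the statistics: "The post baseline value and the percent change from baseline at post baseline are summarized by mean, SD, median, Q1, and Q3". For liver tests, the same section gives the number and percentage of patients who newly meet a stated multiple of the upper limit of normal at any time after treatment. It also says that clinically significant abnormal results are reported as adverse events and appear in the AE tables.

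**The concern.** The endpoint asks how many participants had an important laboratory change. For neutrophils, the planned table answers a different question: where the centre and the middle half of the distribution lie at each visit. Neutropenia affects the lower tail, probably in a minority of patients, and Protocol 4.5 calls the falls transient. Different patients could therefore be low at different visits, which dilutes any single-visit summary further.

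The other route to a patient count is the AE tables. Under Protocol 10.1.1, a laboratory value becomes an adverse event only if it causes signs or symptoms, needs therapy, or is considered clinically significant. No ANC cut-off is attached. At stake is whether the report can state, on an objective and uniform basis, how often a laboratory effect described in the protocol occurred in each arm.

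**Working it through.** The plan states no figure on this point, so there is none to reproduce. The check sets the passages side by side and then asks what the planned statistics can show.

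**1. What is planned for each type of safety measurement**

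| Measurement | Minimum | Patients meeting a numeric criterion |
|---|---|---|
| Continuous data, SAP 2.1 default | yes | not applicable |
| Vital signs, SAP 2.8.3.2 | yes, post-baseline minimum and maximum | no |
| Liver tests, SAP 2.8.2 | maximum used for combined criteria and plot | yes, newly occurring n (%) |
| ANC, SAP 2.8.2 | not listed | no |

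The SAP default applies unless the text says otherwise. Section 2.8.2 gives its own list, which leaves out the minimum and maximum.

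**2. Other places where low values might appear**
- SAP 2.1.1.5 keeps unscheduled values out of by-visit analyses. It admits them to summaries of abnormal findings, but none is visible for hematology.
- SAP 2.1.1.8 mentions notable criteria. None is defined for hematology in the visible text.
- The SAP document history says the laboratory listings were deleted because summary tables had been added.
- Neutropenia is not among the adverse events of special interest in Protocol 12.5.3 or SAP 2.8.1.1.

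**3. Limit on the quartile, without distributional assumptions**
The lower quartile at a visit can fall below 1.0 x 10^9/L only if about a quarter of the patients measured are below it. With 225 measured per arm (450/2), that is 0.25 x 225 = about 56 patients. Below that share, no listed statistic gives the number of low patients.

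**4. Illustration with assumed values (not in the documents)**
One arm of 225, ANC lognormal with median 6 x 10^9/L and coefficient of variation 60%. A share of patients is replaced by values from 0.4 to 0.99. Averages over 4000 simulated arms:

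| Share moved | Mean | Median | Q1 | Minimum | Patients <1.0 |
|---|---|---|---|---|---|
| 0% | 6.99 | 6.01 | 4.14 | 1.31 | about 0 |
| 2% | 6.89 | 5.94 | 4.05 | 0.52 | about 4 |
| 5% | 6.70 | 5.80 | 3.87 | 0.45 | about 11 |
| 10% | 6.38 | 5.58 | 3.55 | 0.43 | about 22 |
| 20% | 5.74 | 5.04 | 2.59 | 0.41 | about 45 |

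A hand check on simpler assumptions (mean 6.0, SD 3.0, 5% falling to 0.8) agrees for the mean. The shift is 0.05 x (6.0 - 0.8) = 0.26, or 0.26/3.0 = 0.09 SD. The standard error of a between-arm difference is 3.0 x sqrt(2/225) = 0.28.

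The mean and lower quartile do move, but a reader could not recover the count from them. The minimum would reveal that a tail exists, and the n (%) would give its size.

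**5. Threshold**
1000/mm3 x 10^6 mm3 per litre = 1.0 x 10^9/L. The exclusion criterion and the level cited in Protocol 4.5 are the same number, so an eligible patient should start at or above it.

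**The case against.** The strongest reply is that the endpoint concerns clinically significant changes, not values below a cut-off, and that the SAP delivers it. Such results go to the AE tables, which count patients by preferred term, severity and relationship to treatment. Protocol 10.1.1 tells investigators to identify them by reviewing out-of-range values and changes from baseline. Infections, the main clinical consequence, have their own tables. The protocol's list of known risks for short-term use does not name neutropenia, and the cardiovascular study showed no imbalance in larger declines between its two doses. ANC, monocytes and lymphocytes are also the cell counts named in the Protocol summary.

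Much of this stands. A reader might infer that low counts would be hidden, or that only means are reported. The documents support neither: the median and quartiles are planned, and a low count judged clinically significant would be counted as an adverse event. A reader might also infer that platelets have been dropped. SAP 2.8.2 does not name them, but its list is introduced as what the parameters include and may not be exhaustive. The table shells are not supplied and SAP 2.9 is redacted, so further tables cannot be excluded.

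What the reply does not supply is an objective count. The AE route depends on judgement without a numeric criterion. For liver tests, the SAP did not consider that route sufficient on its own.

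**Conclusion.** The point holds as a minor gap in descriptive safety reporting. In the visible text, patients with low ANC are counted only through investigator-reported adverse events, while the planned hematology statistics contain neither a minimum nor a threshold count. The primary and key secondary tests are unaffected.

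The size shown rests on assumed ANC values. The conclusion that quartiles cannot give a count below about a 25% share does not.

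The case is weaker for platelets and other tests. The documents give no analysis threshold for platelets, and they leave unclear which results are available. Table 8-1 marks hematology and chemistry for the database, whereas SAP 2.8.2 singles out liver results as those to be entered. It would therefore be too strong to say that all these data are in hand. ANC must be, because SAP 2.8.2 already summarises it.

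**What to change.** In SAP 2.8.2:
- Extend the newly occurring n (%) rule used for liver tests to post-baseline ANC <1.0 x 10^9/L. Use all post-baseline values, including unscheduled visits, as SAP 2.1.1.5 allows. Take patients with at least one post-baseline ANC as the denominator.
- Report the minimum post-baseline ANC by arm.
- Reconcile the section with Protocol 8.4.1.2 and 12.5.3. Either summarise platelets and the other collected tests by treatment and visit where they are in the database, or declare the narrowing in SAP section 4.

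The cost is one or two extra descriptive safety tables. The ANC part needs no new data collection. The platelet and other-test part first needs a check of what was entered. There is no effect on the primary test or on alpha.

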## **2.8.3 Other safety data**

### **2.8.3.1 SARS-CoV-2 Virus test**

[figure not shown]
The presence of SARS-CoV-2 virus will be tested by central lab based on nasopharyngeal samples taken at baseline and at discharge from hospital/Day 29 if not discharged.

[figure not shown]
A summary on viral load by sequential quantitative RT-PCR for SARS associate coronavirus will be summarized by geometric mean at baseline, at discharge for those who are discharged on or before Day 29, at Day 29 for those who are not discharged on or before Day 29. The summary will also be provided by the day interval between Day 1 to discharge from hospital: Discharge on Day 1 to Day 7, discharge on Day 8 to Day 14, Discharge on Day 15-Day 21, Discharge on Day 21 to Day 29.

[figure not shown]
In addition, a summary on number (%) of patients with positive (a reading  $\geq$ LLOQ) or negative ( $<$ LLOQ) test results will be provided at baseline, at discharge for those who are discharged on or before Day 29, at Day 29 for those who are not discharged on or before Day 29, and by the discharge day interval.

### **2.8.3.2 Vital signs**

Vital sign measurements include respiratory rate, pulse rate, systolic and diastolic blood pressure, and body temperature. Absolute values and change from baseline will be summarized for each of the aforementioned vital sign parameters by treatment group, visit and time point including the minimum and maximum Post-baseline value.

[figure not shown]

## **2.10 Interim analysis**

Summaries of safety data will be produced for DMC safety monitoring when needed.

## **3 Sample size calculation**

### **3.1.1 Primary endpoint**

Approximately 450 patients will be randomized to canakinumab + SOC or placebo + SOC in a 1:1 ratio.

Patients infected with COVID-19 exhibit a wide range of clinical severity. With recent initial outbreak and evolving pandemic situations, limited data is available to precisely estimate the rate of disease progression after hospital admission for the population of interest under SOC. The CDC reported 31.4% hospitalizations and 11.5% ICU admissions (among patients with known hospitalization and ICU admission status) in the United States between February 12 and March 16, 2020 ([CDC COVID Response Team 2020](#)). An earlier summary ([Wu and McGoogan 2020](#)) of 72314 diagnosed cases in China estimated about 81% mild cases, 14% severe cases, 5% critical case and an overall case-fatality rate of 2.3%. A worldwide tally by WHO as of March 12th, 2020 estimated a mortality rate of 3.7% with 125,048 confirmed cases. A study by [Zhou et al \(2020\)](#) based on complete follow-up of 191 in-hospital patients during the early outbreak of COVID-19 in China reported an in-hospital CFR as high as 28%, while other studies

reported much smaller CFR with incomplete follow-up data. Detailed summaries of disease progression time course during hospitalization or by disease status based on large samples, however, were not found.

With this study enrolling only hospitalized patients with COVID-19 induced pneumonia and CRS, and assuming that more than half of this patient population will likely require invasive mechanical ventilation, the true response rate for the control arm of this study is considered most likely in the range from 20% - 50%, while the CFR is not likely to be more than 25%.

Invasive mechanical ventilation is a radical departure from the physiology of breathing spontaneously, which put patients under risks of various immediate and long-term complications ([Soni and Williams 2008](#)) regardless of the survival outcome. The benefits of canakinumab for COVID-19 patients is considered clinically meaningful if it leads to an absolute increase of 15% patients who survived without ever requiring invasive mechanical ventilation. A 4-week CFR reduction by half (i.e. relative risk=0.5) is also considered meaningful clinical benefit outweighing the known risks of canakinumab.

Assuming the true response rate for the control arm lies within the range of 20% - 50%, a total sample size of 450 and 1:1 randomization ratio will provide at least 89% power to detect the minimum clinically meaningful benefit of interest.

**Table 3-1 Power for primary analysis under varying assumptions (sample size = 450)**

Response Rate (%)		Clinically meaningful benefits			Power (2-side $\alpha=0.05$ )
Control	ACZ885	difference	OR	RR	
50	65	15	1.86	1.3	89%
40	55	15	1.83	1.38	89%
30	45	15	1.91	1.5	90%
20	35	15	2.15	1.75	94%

Early discontinuation from study before patient recovery is considered unlikely in this study, hence the sample size is not adjusted for attrition. Blinded sample size reevaluation may be performed to confirm the assumptions for the sample size calculation, based on which the sample size may be updated without inflation of type I error.

